##### 15.5.1.3 STEP 5A-2: INTERVENTION GROUP ASSIGNMENT

If participant is assigned to the intervention group (GogyUp Reader App), state:

*Ok – you've been assigned to the GogyUp Reader app group.*

*Do you have a device – either a mobile phone, tablet, or computer, that you can access regularly? Does this device have regular internet access?*

*If so, we will send you a \$25 gift card to help cover the cost of your network access during the study after you've completed a baseline assessment. Once you complete a follow-up assessment at the end of the three months, we will send you another \$25 gift card to thank you for your participation..*

If participant mentions that they do not have internet cell service or access to a computer or mobile device, explain that we can provision a internet-connected tablet while they are enrolled in the study.

---

15.5.1.4      STEP 5B: SCHEDULE FOLLOW-UP APPOINTMENT AND BASELINE ASSESSMENT

*The very last items we need to do is to set up an appointment to take a survey together to help establish some base line information.*

If there is enough time and the participant is willing, conduct the baseline assessment now. Otherwise, set up baseline and follow-up assessment appointments.

**Note for Intervention Group Participants:**

- If participant is in Intervention group, explain that the data plan compensation or tablet will be sent once the baseline assessment has occurred.

*Ok – great! Next, we need to set up a time to meet for 10 – 15 minutes to take a survey together. If you have the time, we could do that now. Otherwise, what days and times would work with your schedule?*

*Again, thank you so much for joining the study. Over the next few months, always free to contact me if you have any questions about the study, how to access GogyUp Reader, etc..*

**IMPORTANT:** Assign the participant a study number and note the assignment in the candidate's record in the JotForm database and whether to follow up.

You will need the participant's study number for the GogyUp training.

15.6 STEP 6: BASELINE ASSESSMENT AND PROCEDURES

**Notes:**

- A participant's ability to follow through and keep the baseline assessment appointment may indicate whether the participant will remain active or become inactive.
- For participants in the control group, education materials should be mailed once the baseline assessment is confirmed. Ideally, the follow-up appointment should be confirmed as well.
- For participants in either group who miss their baseline assessment appointment, at least three attempts (which can be a mix of voice call / voicemail and SMS messages) should be made to contact and reschedule.
- For participants in the intervention (GogyUp Reader) group, data plan reimbursement should be made available only after the baseline assessment has been completed and a follow-up appointment has been confirmed.
  - If a participant mentions they do not have internet access or an internet-enabled device, notify GogyUp's administrative assistant to provision a tablet for the participant.
- After the baseline assessment is complete, follow the script for onboarding participants in the intervention group.

---

#### 15.6.1 1 DAY BASELINE ASSESSMENT – SMS APPOINTMENT REMINDER

*Hi, this is [your name] – the GogyUp Research Coordinator.*

*I'm looking forward to taking the survey together on [APPOINTMENT DATE AND TIME]. We're planning to meet [ Online / Over the phone ].*

*If the participant signed up for an online meeting, text the link. Otherwise confirm you'll call them at this phone number.*

*Here is the link for us to meet: [ ZOOM LINK ].*

*Record each contact attempt must in the participant's database record.*

---

#### 15.6.2 SCRIPT FOR BASELINE ASSESSMENT - PHONE OR ONLINE MEETING

*If the baseline assessment appointment is schedule as a phone meeting:*

*Hello. This is [YOUR NAME] FROM GogyUp. Is [NAME OF PARTICIPANT] available?*

*Wait for confirmation that you are speaking with the participant.*

*I am calling to take our GogyUp / University of Minnesota Type 2 Diabetes survey with you. Is this still a good time?*

*Wait for confirmation that participant is ready, then explain why we're administering the assessment.*

# RCT of Assistive-Reading Technology for Post-Visit Type 2 Diabetes Patient Education

Version 1.4

Protocol 1

10 February 2023

Great! Ok – the reason why we’re taking this questionnaire now is to establish every participant’s current understanding of health and diabetes.

Before we begin, do you have any questions for me about the survey or the study?

Answer any questions that the participant has, referring to the Study Disclosure Document as necessary.

Questions that cannot be addressed by the Study Disclosure Document should be forwarded to the Primary Investigators.

If you’re meeting via Zoom, display the JotForm Baseline Assessment form and administer the Health Literacy Questionnaire (HLQ) and Baseline Demographic Questions according to the directions in the JotForm form. Record participant score in the JotForm form. Add any other notable questions asked to the comments area in the participant’s database area.

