### 9.1 ENDPOINT AND OTHER NON-SAFETY ASSESSMENTS

Assessments for this study will include eligibility assessment and initial contact for pre-screening, as well as baseline and follow-up measures. We will also extract internal app data for the study period to assess adherence in the intervention arm (and to ensure no contamination in the control arm).

To ensure a focus on equitable representation and on a sample reflective of our interest in low income (publicly or non-insured) patients, the study team and health system research support staff determined that initial contact with recruiting materials (see above) will be prioritized to individuals seen at primary care clinics in the health system that see the largest proportions of publicly insured or non-insured patients. Iterative mailings will continue to prioritize patients from these clinics as well as patients in historically excluded and underrepresented groups (e.g., Black or Indigenous patients) among those fitting initial eligibility criteria (see above). Health system staff will conduct pre-screening procedures including identifying a potential sample and sending recruitment mailings (see Recruitment Collateral below). To ensure candidates are fully opted-in, GogyUp and study staff will not have access to any potential participants until participants contact GogyUp by filling out an online intake form or calling, texting, or emailing the GogyUp Research Coordinator through a study-designated phone number and email address listed on the recruitment letter.

Once eligible participants are consented by the GogyUp Research Coordinator, enrollment and baseline assessments will take place within an expected two-week (maximum) timeframe. Baseline assessments will include study staff administration (remotely via phone or video call) of the validated Health Literacy Questionnaire subscales 9 and 2, "Understanding health information" and "Having sufficient information," as well as the secondary outcome of the PDSMS. At three months post-baseline, study staff will conduct follow-up administration of the same outcomes. Based on our theoretical mechanism of action (see above), health literacy is the primary set of

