#### 10.4.2 ANALYSIS OF THE PRIMARY ENDPOINT(S)

We will specify the primary outcome as three-month follow-up level of the Health Literacy Questionnaire subscales 9 and 2 (understanding written information and having enough in enough information) as single endpoints (not repeated measures)..

We will compare the mean outcomes at follow-up between the treatment arms using analysis of covariance (ANCOVA), which compares follow-up outcome values between study arms while controlling for the baseline levels to gain power to detect an effect. The primary analysis will be an intent-to-treat (ITT); for non-monotonic missing (e.g., missing a baseline value), we will use multiple imputation with pattern mixture model adjustments in sensitivity analyses allowing for plausible differences among the missing—the justification for this is that pattern mixture models allow for a Missing Not At Random assumption, which is plausible in this case because we will not have measures for all likely variables associated with missingness. Pattern mixture models allow for us to set plausible values for missingness at both high or low levels to obtain a range of outcome estimates allowing for plausible missing data scenarios. For any monotonic missing—i.e., attrition (withdrawal or other lost to follow-up), we will use last observation carried forward but will also conduct sensitivity analyses using pattern mixture models under plausible assumptions of missing data patterns. We will present results using adjusted (least-squares) means with standard errors, p-values, and 95% confidence intervals. Baseline levels of endpoint outcomes will be included as a covariate to gain power to detect an effect, a standard use of ANCOVA.

---

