### 15.8.2 SCRIPT FOR FOLLOW-UP ASSESSMENT - PHONE OR ONLINE MEETING

If the follow-up assessment appointment is schedule as a phone meeting:

*Hello. This is [YOUR NAME] FROM GogyUp. Is [NAME OF PARTICIPANT] available?*

*Wait for confirmation that you are speaking with the participant.*

*I am calling to take our GogyUp / University of Minnesota Type 2 Diabetes survey with you. Is this still a good time?*

*Wait for confirmation that participant is ready, then explain why we're administering the assessment.*

*Great! Before we begin, do you have any questions for me about the survey or the study?*

Answer questions that the participant has, referring to the Online Disclosure Document as necessary.

Display the JotForm assessment.

Administer the HLQ and PDSMS according to directions posted on the JotForm site.

For participants in the intervention group, administer the User Experience Questions after the HLQ and PDSMS. Record participant scores using the online form. If the participant asks additional questions or provides additional feedback, record in the comments area of the participant's database record.

---

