## 15.9 BASELINE AND FOLLOW-UP ASSESSMENTS

The majority of the Baseline and Follow-Up Assessments is the 44 question Health Literacy Questionnaire (HLQ) divided into 2 sections. Each assessment will begin with a landing page (sample below) to help orient the participant. Following the landing page, the participant will be presented with each section of the HLQ. The research coordinator will read each HLQ question and record the participant's response.

The Baseline Assessment also has a demographic that serves a few purposes:

- 1) Capture important information that may have dissuaded candidates from initially enrolling (e.g., gender, age, preferred language, etc.) but would allow the team to compare any intervention effect across different sub-groups.
- 2) Pilot a question concerning whether GogyUp impacts a participant's confidence in using a smartphone or tablet to learn new health information.
- 3) In addition to the HLQ, the Follow-Up Assessment includes the Perceived Diabetes Self-Management Scale (PSDMS) and 14 questions to capture end-user Gather information about the user experience for GogyUp's development team (administered to the GogyUp Reader group only).

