## 15.9.5 FOLLOW-UP: PERCEIVED DIABETES SELF-MANAGEMENT SCALE (PSDMS)

INSTRUCTIONS: This is a questionnaire designed to determine how well you, yourself, feel you manage your diabetes. Each item is a belief statement with which you may agree or disagree. Next to each statement is a scale which ranges from strongly disagree to strongly agree. Please respond to each of the following items by choosing one number for each statement. Try to respond to each statement separately in your mind from each other statement. Choose your responses thoughtfully and make them as true FOR YOU as you can. Please respond to every statement.

1. It is difficult for me to find effective solutions for problems that occur with managing my diabetes.
  - c Strongly disagree
  - c Disagree
  - c Neutral
  - c Agree
  - c Strongly agree
2. It is difficult for me to find effective solutions for problems that occur with managing my diabetes.
  - c Strongly disagree
  - c Disagree
  - c Neutral
  - c Agree
  - c Strongly agree
3. I handle myself well with respect to my diabetes.
  - c Strongly disagree
  - c Disagree
  - c Neutral
  - c Agree
  - c Strongly agree
4. I am able to manage things related to my diabetes as well as most other people.
  - c Strongly disagree
  - c Disagree
  - c Neutral
  - c Agree
  - c Strongly agree
5. I succeed in the projects I undertake to manage my diabetes.
  - c Strongly disagree
  - c Disagree
  - c Neutral
  - c Agree
  - c Strongly agree
6. Typically, my plans for managing my diabetes don't work out well.
  - c Strongly disagree
  - c Disagree
  - c Neutral
  - c Agree
  - c Strongly agree

RCT of Assistive-Reading Technology for Post-Visit Type 2 Diabetes Patient Education

Version 1.4

Protocol 1

10 February 2023

7. No matter how hard I try, managing my diabetes doesn't turn out the way I would like.

c Strongly disagree

c Disagree

c Neutral

c Agree

c Strongly agree

8. I'm generally able to accomplish my goals with respect to managing my diabetes.

c Strongly disagree

c Disagree

c Neutral

c Agree

c Strongly agree

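### Section 9.1 requires the PDSMS at baseline, but the baseline script, section 15.9 and the only printed form give it only at follow-up; if staff follow these, H3 has no baseline for its planned analysis

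*Combined protocol and SAP*

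**What the plan says.** On collection, section 9.1 lists the two HLQ subscales at baseline "as well as the secondary outcome of the PDSMS", and adds that at three months "study staff will conduct follow-up administration of the same outcomes". The Schedule of Activities (2.3) marks outcomes assessments at Visit 1 and Visit 2, without naming instruments.

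The operational text reads differently. The baseline script (15.6.2) tells the coordinator to "administer the Health Literacy Questionnaire (HLQ) and Baseline Demographic Questions according to the directions in the JotForm form". The matching follow-up script (15.8.2) says "Administer the HLQ and PDSMS according to directions posted on the JotForm site". Section 15.9 describes the baseline assessment as the HLQ plus demographic questions, and then states: "In addition to the HLQ, the Follow-Up Assessment includes the Perceived Diabetes Self-Management Scale (PSDMS". The one PDSMS form printed in the document, 15.9.5, is headed "FOLLOW-UP: PERCEIVED DIABETES SELF-MANAGEMENT SCALE (PSDMS". (The document spells the abbreviation both PDSMS and PSDMS.)

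On analysis, 10.4.3 applies the primary-endpoint model and missing-data approach to the PDSMS. Under 10.4.2 this means ANCOVA, where "Baseline levels of endpoint outcomes will be included as a covariate to gain power to detect an effect", and for attrition "we will use last observation carried forward". For non-monotone gaps, with a missing baseline value as the example, 10.4.2 gives multiple imputation. Section 10.4.5 tabulates the baseline levels of the endpoints.

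**The concern.** Staff will work from the scripts. Section 9.1 relies on standard scripts for both appointments and requires no specific training or degree of the assessors. Section 10 says there is no separate SAP, so no other analysis document settles the conflict.

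If the scripts are followed as printed, no participant in either arm has a baseline PDSMS. The analysis planned for H3 then cannot be run as written, and a baseline that was not taken cannot be recovered later. Section 10.2 also promises that participants who withdraw or are lost will be included in the analysis. For H3 that promise rests on a baseline value that may not exist.

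**Working it through.** **1. The passages side by side**

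| Place | Baseline | Follow-up |
|---|---|---|
| 9.1 | PDSMS named | same outcomes repeated |
| 2.3 Schedule of Activities | outcomes assessments marked, instruments not named | same |
| 15.6.2 / 15.8.2 scripts | HLQ and demographics only | HLQ and PDSMS |
| 15.8 notes | – | HLQ and PDSMS, both arms |
| 15.9 | HLQ and demographics | HLQ and PDSMS |
| 15.9.5 printed form | – | headed as a follow-up form |
| 11.1.4 Steps 6 / 8 | HLQ and demographics | HLQ only |

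The two scripts are the most telling pair. HLQ in the baseline script does not read as shorthand for all outcomes, because the follow-up script names the HLQ and the PDSMS separately. Step 6 is weak evidence: Step 8 also omits the PDSMS at follow-up, where 15.8 and 15.8.2 clearly require it.

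**2. What each analysis step needs if no participant has a baseline PDSMS**

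- ANCOVA (10.4.2, 10.4.3): needs the baseline value as covariate. Not available.
- LOCF for dropouts: with a single follow-up, baseline is the only earlier observation. Nothing to carry.
- Multiple imputation of a missing baseline: needs some observed baseline PDSMS values to fit the imputation model. None.
- Baseline table (10.4.5): PDSMS row empty.

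**3. The plan's own power figures**

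Inputs from 10.2, 10.4.1 and 5.1.3: 80 per arm at SMD 0.4; 60 per arm at SMD 0.5; two-sided 0.05; 1:1. The two-sample t-test is stated in 10.2 for the Understanding subscale and is applied here to the PDSMS.

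Normal approximation: power = Φ(d·√(n/2) − 1.96).

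- 80 per arm: 0.4 × √40 = 2.530; Φ(0.570) = 71.6%. Plan: 72%.
- 60 per arm: 0.5 × √30 = 2.739; Φ(0.779) = 78.2%. Plan: 78%.

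The noncentral t gives 71.0% and 77.5%. The stated figures are reproduced without any baseline adjustment.

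**4. What adjustment would add**

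ANCOVA on a baseline with correlation r to follow-up raises the effective SMD to d/√(1 − r²). The documents give no r, so a range is assumed. At 80 per arm and SMD 0.4, noncentral t with 2n − 3 degrees of freedom:

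| Assumed r | Effective SMD | Power | Unadjusted n per arm with equal precision, 80/(1 − r²) |
|---|---|---|---|
| none | 0.400 | 71% | 80 |
| 0.3 | 0.419 | 75% | 88 |
| 0.5 | 0.462 | 83% | 107 |
| 0.7 | 0.560 | 94% | 157 |

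**5. What a substitute covariate could recover**

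With baseline HLQ subscales 9 and 2 as covariates, the effective SMD is d/√(1 − R²) with 2n − 4 degrees of freedom. If they explain an assumed 4%, 9% or 16% of the follow-up PDSMS variance, power is 73%, 75% or 78%.

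**The case against.** The strongest reply is that the protocol body is consistent. Section 9.1, the Schedule of Activities, 10.4.2, 10.4.3 and 10.4.5 all point to baseline outcome collection, so this looks like a script omission rather than an unsettled design. The script also defers to the JotForm directions, and the live baseline form, which is not reproduced, may contain the PDSMS. Section 15.9 is poorly drafted too: its sentence about the follow-up assessment sits in a list of purposes of the baseline demographic section. All of this stands. It shows which direction of repair is more natural and limits what can be claimed, but it does not remove the contradiction.

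A second reply is that 10.4.2 already handles a missing baseline by multiple imputation. This holds if only some participants lack the value. It fails if all do.

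A third is that H3 is one secondary endpoint in a pilot and an unadjusted comparison at follow-up remains possible. That is also true, and it caps the importance of the point.

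Some stronger conclusions are tempting but not supported:

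- A reader might infer that the baseline PDSMS was certainly not collected. The documents do not show the live form, nor that anyone was enrolled under these scripts.
- A reader might infer that the stated PDSMS powers are wrong. They come from an unadjusted comparison and never relied on a baseline.
- A reader might infer that losing LOCF lowers power. A carried-forward baseline contains no treatment effect, so with an assumed 20% random dropout, equal in both arms, LOCF would shrink an effect of 0.40 to 0.40 × 0.80 = 0.32. The harm is that the planned rule cannot be applied.

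**Conclusion.** The contradiction on when the PDSMS is collected is certain. That the baseline will go uncollected is likely if staff follow the scripts, but cannot be established from the documents.

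In that event the H3 ANCOVA, its handling of dropouts and its row in the baseline table cannot be produced as planned. With full follow-up, the cost in power at 80 per arm and SMD 0.4 is the gap between about 71% and 75% to 94%. That range depends entirely on assumed correlations of 0.3 to 0.7. The stated 72% and 78% remain correct with full follow-up. Both HLQ primary endpoints are unaffected, because the HLQ is given at baseline.

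The point is worth fixing because the repair is small and the missing value cannot be obtained afterwards.

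**What to change.** Reconcile the passages, preferably in line with 9.1 and the Schedule of Activities:

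- Add the PDSMS to the baseline form (printed and live), 15.6.2, Step 6 of 11.1.4 and 15.9, for both arms.
- Retitle 15.9.5 as a baseline and follow-up form.
- Add the PDSMS to Step 8, which omits it at follow-up.

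Check the live baseline form first, since it shows whether any data are at risk. Then:

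- If only some participants lack a baseline PDSMS, apply the multiple imputation already stated in 10.4.2, within one model for the whole intention-to-treat set.
- If none has it, amend 9.1, 10.4.3 and 10.4.5 and prespecify one H3 model for the whole intention-to-treat set, for example ANCOVA on baseline HLQ subscales 9 and 2. Replace LOCF for dropouts with a rule that needs no baseline PDSMS, such as multiple imputation from those subscales, keeping the pattern-mixture sensitivity analyses of 10.4.2.

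The cost is an IRB-reviewed script and form amendment and a slightly longer baseline call (eight items). If no baseline PDSMS is intended, only the text changes, and the adjustment gain is given up apart from what the HLQ subscales recover.

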## 15.6.3 BOTH GROUPS – CONFIRM FOLLOW-UP APPOINTMENT AND SCHEDULE FOLLOW-UP ASSESSMENT

Make every effort to schedule and confirm their follow-up assessment appointment. Display the scheduling page to provide 3 to 4 options for the participant to choose from.

*We have scheduled our follow-up call for [ TIME and DATE of APPOINTMENT]. Is that still convenient?*

## 15.6.4 FOR INTERVENTION GROUP (GOGYUP READER) PARTICIPANTS

If participant is in the GogyUp Reader group, explain the first gift card to reimburse network access will be mailed in the next day or so. Confirm the mailing address.

If the participant requested to use a tablet, explain that it should arrive in a few days and confirm that the mailing address can securely receive packages.

*Lastly, I want to make sure we have the best address to send the [ TABLET / DATA PLAN REIMBURSEMENT / DIABETES HEALTH MATERIALS ] to you. I have [ PROVIDE THE PARTICIPANT’S ADDRESS ] – is that the correct location to send it?*

Thank the participant for their time. Note interactions, questions, and appointments in the participant’s database record.

#### 15.6.5 FOR CONTROL GROUP (PAPER DOCUMENTS) PARTICIPANTS

If participant is in the control group, confirm the mailing address to receive the packet of materials.

*Lastly, I want to make sure we have the best address to send the DIABETES HEALTH MATERIALS to you. I have [ PROVIDE THE PARTICIPANT'S ADDRESS ] – is that the correct location to send it?*

Thank the participant for their time. Note interactions, questions, and appointments in the participant's database record.

---

